#### ***Data captured through phone call, SMS or home visit to caregivers***

Research assistants will be trained to administer a simple questionnaire by phone to caregivers of all children at day 7 (range 6-14 to accommodate weekends and multiple attempts and home visits to those caregivers who do not have a phone or phone number) after their initial consultation with a HW of participating facilities, regardless of re-attendance visits. If the first phone follow-up fails, up to four additional attempts will be made on the subsequent days, after which they will be deemed lost to follow-up. These research assistants will be placed in a call center outside of the HF and blinded to which facility the child has attended as much as possible. Data recorded during these phone interviews will be collected electronically and sent at least once a day to the central server. For the question related to the clinical primary outcome measure (percentage of children cured at day 7), field workers will be particularly trained not to influence caregivers when they answer the questions “Is the child cured?” and insist that they simply answer “Yes” or “No”. If the answer is “No”, the caregiver will be strongly advised to re-attend a HF, if possible, the one they went to for the initial consultation. Same procedure will be implemented if home visits are required using a REDCap mobile application. The questions included in the phone/SMS/home visit questionnaire are listed in **Appendix A**.

Concurrently with the personal phone call follow-up system, automated phone call and SMS systems with the same questions will be tested during the pilot or in Phase 1 in a subset of patients to check for congruency between the answers obtained using both methods. If an automated system proves successful, it will be implemented in all facilities. With the automated system, if no response is received from the first call or SMS sent to the caregiver, the research assistant will make up to two follow-up calls before the patient is deemed lost to follow-up.

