2.1.2 Secondary outcomes

All secondary outcomes are compared between the intervention (ePOCT+) and control (routine care) arms.

Percentage of children cured at day 7 in the intervention group (ePOCT+) as compared to the control group (routine care)

Outcome measure: The child is defined as being cured at day 7 if the caregiver says that the child is cured or has improved since the initial consultation. Non-referred secondary hospitalizations (if caregiver says that child was hospitalized between day 0 and day 7 but the electronic clinical data does not indicate a referral for hospitalization) will however be considered as clinical failures even if the child is already cured at day 7.

Timing and method of measurement: Assessment of subjective clinical cure by the caregiver, and history of non-referred hospitalization will be assessed by telephone or home visit follow-up 7 days (range 6-14 days) after enrollment of the subject. The day of enrollment of the subject is considered as day 0.

Analysis type: Superiority

Secondary consultations:

- % of children with one or more unscheduled re-attendance visits at any health facility by day 7

Timing and method of measurement: Telephone or home visit follow-up 7 days (range 6-14 days) after enrollment of the subject. The day of enrollment of the subject is considered as day 0.

Severe outcome by day 7:

- % of children with non-referred secondary hospitalization by day 7
- % of children who have died by day 7

Timing and method of measurement: Death and non-referred secondary hospitalization will be assessed by telephone or home visit follow-up 7 days (range 6-14 days) after enrollment of the subject. The day of enrollment of the subject is considered as day 0.

Primary referrals:

- % of children referred to hospital or inpatient ward at a health centre at initial consultation

Timing and method of measurement: Documented by the HW at the end of the initial consultation in the eCRF (control arm) or in ePOCT+ (intervention arm) when the subject was enrolled (day 0)

Appropriate case management for malaria at initial consultation

- % of febrile children tested for malaria by RDT and/or microscopy at day 0
- % of malaria positive children (positive RDT result OR positive microscopy result) prescribed an antimalarial at day 0
- % of malaria negative children prescribed an antimalarial at day 0
- % of untested children prescribed an antimalarial at day 0

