Effect modification of the primary outcome of antibiotic prescription will be performed in groups of patients where the highest reduction in antibiotic prescription is expected, and areas of extension of the content of the algorithm compared to the version tested in the previous ePOCT study. Effect modification by sex, age group (young infants ages 1 to 59 days, children aged 2 months to 5 years, and children aged 5 to 14 years), respiratory symptoms, fever without clinical source, gastrointestinal complaints (vomiting and diarrhea), skin problems, ear, nose and throat problems, will be assessed by incorporating an interaction term between the treatment arm and the respective variable, acknowledging that power will be low. Furthermore in order to adjust for potential imbalances in baseline characteristics between study groups, relevant baseline characteristics will be included as fixed effect variables in the final model. Baseline characteristic imbalance will be determined by statistical method (i.e., comparisons of treatment arms over all clusters and within clusters) and by consensus among the study analysis team.

The number of children lost to follow up may be quite high due to the difficult nature of phone follow-up at day 7, as found in previous studies with day 7 phone call lost to follow up rates of 13-25% (Christie et al., 2018; Hannigan, Chisale, Drew, Watson, & Gallagher, 2019; Nguhuni et al., 2017).

Comparatively, the proportion not cured at day 7 is expected to be quite low (3%). The use of a complete case analysis was therefore selected for the secondary outcome of day 7 clinical cure, as it would be the most conservative analysis. If we were to use the “enrolled set” and considered all day 7 lost to follow up as not being cured, this would dilute the difference between arms. Not considering lost to follow up cases as failures is also the approach used for similar studies with high number of LTF

and low proportion of outcomes (Källander et al., 2018). We may adjust the final model for further baseline variables (not already included as fixed effect variables) which are associated with missing outcome data (analogous to performing multiple imputation in the case of a single endpoint). As with the other fixed effect variables, baseline characteristic imbalances among patients lost to follow up will be determined by consensus among the study analysis team.

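### The protocol lets automated calls or SMS replace interviewer day-7 calls, possibly within Phase 1, on a congruency check with no stated criterion and with fewer contact attempts

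*Protocol*

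**What the plan says.** **Protocol 8.1.6** (data captured through phone call, SMS or home visit). Research assistants phone all caregivers at day 7 (range 6-14). If the first call fails, "up to four additional attempts will be made on the subsequent days", which makes five in all. Caregivers without a phone are visited at home. Alongside this, automated calls and SMS that put an identical questionnaire "will be tested during the pilot or in Phase 1 in a subset of patients to check for congruency between the answers". The text continues: "If an automated system proves successful, it will be implemented in all facilities". Under the automated system, a caregiver who does not respond to the first contact gets "up to two follow-up calls before the patient is deemed lost to follow-up", so three attempts in all, the last two by a research assistant.

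**Other places that define the Phase 1 mode:**

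- Protocol synopsis, procedures and measurements: the Phase 1 questionnaire is given to all caregivers by phone. Automated calls or SMS are named only as a Phase 2 departure, dependent on resources.
- Protocol 4.1, and the outcome lists in the synopsis and 7.1: phone call, SMS or home visit.
- SAP 2.1.2: cure and non-referred hospitalisation "will be assessed by telephone or home visit follow-up 7 days (range 6-14 days) after enrollment of the subject". Death is measured the same way.
- SAP 3.1: phone call or home visit.

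The SAP mentions neither SMS nor automated contact and plans no analysis by follow-up mode. SAP 6.1 expects 3% not cured, cites 13-25% loss for day-7 phone follow-up in earlier studies, and analyses cure on complete cases.

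**The concern.** Day-7 cure, non-referred hospitalisation and death carry most of the weight behind the hypothesis that antibiotic use falls while clinical outcomes stay similar. As 8.1.6 is worded, the instrument for these outcomes could change between or within the Phase 1 blocks.

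Three features make this more than missing detail. First, the only named test is congruency, and when 97% of children are expected to be cured, simple agreement says little about whether failures are found. Second, congruency can be observed only in caregivers who answer both systems, so it does not speak to non-response. Third, the number of contact attempts falls when the mode changes.

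Under-detection that is equal in both arms does not cancel out in a comparison meant to show no harm. It shrinks the risk difference and so favours a finding of similarity. A partial switch would also make the pooled cure result a mixture of two instruments, with nothing in the SAP to separate them.

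**Working it through.** The documents give no figure for validating the automated system, so there is none to reproduce.

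**Inputs from the documents:** failure rate q = 3% and cited loss 13-25% (SAP 6.1); attempts 5 and 3 (Protocol 8.1.6); 660 children per cluster and 16 clusters per arm (SAP 3.3).

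**Assumptions:** sensitivity (Se) 60% and specificity (Sp) 99% of the automated answer, with the interviewer answer as reference; a true 3.0% versus 4.5% not cured; equal and independent contact chances per attempt.

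**1. Agreement** = q·Se + (1−q)·Sp. Kappa = (agreement − chance)/(1 − chance).

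| System | Agreement | Kappa |
|---|---|---|
| Logs every child as cured (Se 0, Sp 1) | 0.97 × 1 = 97.0% | 0 |
| Se 0.6, Sp 1 | 0.018 + 0.97 = 98.8% | 0.74 |
| Se 0.6, Sp 0.99 | 0.018 + 0.9603 = 97.8% | 0.61 |

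For the last row, chance agreement is 0.03 × 0.0277 + 0.97 × 0.9723 = 0.944, so kappa = (0.9783 − 0.9440)/(1 − 0.9440) = 0.61. A 95% or 97% agreement rule would pass all three systems. A rule of 99% agreement or of kappa ≥ 0.8 would reject all three.

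**2. Effect on the comparison if all calls were replaced.** Observed rate = q·Se + (1−q)·(1−Sp).

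- At 3.0%: 0.018 + 0.0097 = 2.77%.
- At 4.5%: 0.027 + 0.00955 = 3.66%.
- Risk difference: 1.5 points becomes 0.885. The share kept is Se + Sp − 1 = 0.59, so 41% is lost.
- Odds ratio: (0.045/0.955)/(0.03/0.97) = 1.52 becomes (0.03655/0.96345)/(0.0277/0.9723) = 1.33.

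With no false alarms (Sp = 1) the rates are 1.8% and 2.7%, and the odds ratio is (0.027/0.973)/(0.018/0.982) = 1.51, almost unchanged. The cost is then precision: at 16 × 660 = 10,560 children, recorded failures in the 3% arm fall from 317 to 190.

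**3. Partial switch.** If one of three equal blocks switched, the loss of risk difference would be about 41%/3 = 14%.

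**4. Attempts.** With equal independent chances, loss after k attempts is (1−r)^k, so three-attempt loss = (five-attempt loss)^(3/5).

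- 0.13^0.6 = 0.29.
- 0.25^0.6 = 0.44.

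**The case against.** **The protocol does not say that raw agreement will be used.** This stands. A stricter statistic would reject the example system, and 8.1.6 does not say that congruency is the sole ground for success. An exact McNemar test on 1,000 children would detect a 40% miss rate 98% of the time if there were no false alarms. That protection is fragile: with 1% false alarms, misses (1.2% of children) and false alarms (0.97%) nearly balance and detection falls to about 5%. A reader might infer that a system missing 40% or more of failures would be approved. The documents do not support that, because they set no criterion. It could be approved; no more can be said.

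**The switch may never reach Phase 1.** This also stands. Testing may end in the pilot, roll-out may wait for Phase 2 as the synopsis procedures suggest, and the SAP already names telephone or home visit. A reader might infer that the Phase 1 outcome will be blunted mid-trial; the text only permits it. But 8.1.6 does not restrict roll-out to Phase 2, and 4.1 and 7.1 allow SMS in Phase 1, so the conflict remains.

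**The SAP reports odds ratios, and these barely move when failures are only missed.** Correct, as shown above. The fall to 1.33 needs the added false alarms as well as full replacement of calls.

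**There is no bias by arm from the roll-out itself.** Correct: it covers all facilities, and each block holds both arms. The concern is equal under-detection.

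**Interviewers are not a gold standard.** Fair. Section 8.1.6 itself trains callers not to influence answers, so disagreement need not mean that the automated system is wrong.

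**The lower attempt count is softened.** Two of the three attempts are still personal calls, and home visits are not withdrawn. Equal reach per attempt is an assumption.

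**Other safety information exists.** Re-attendance at participating facilities is recorded electronically whatever the call mode, so day-7 contact is not the only evidence on harm.

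**Conclusion.** The point holds as a conflict over the Phase 1 measurement mode and an undefined approval rule. Section 8.1.6 permits a change of day-7 instrument during Phase 1, with attempts cut from up to five to up to three. The synopsis procedures and the SAP describe something else.

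At the SAP's 3% failure rate, raw agreement could pass a poor system: 97.0% for one that finds no failures, and 97.8% at the assumed sensitivity of 60% and specificity of 99%. If that system replaced every call, a true 3.0% versus 4.5% would appear as 2.8% versus 3.7%, with the odds ratio falling from 1.52 to about 1.33. Without false alarms the odds ratio is nearly unchanged and the loss is in precision. A switch in only some blocks would have a proportionally smaller effect.

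Three attempts instead of five would turn 13-25% loss into about 29-44% in a complete-case analysis, if the cited range is the five-attempt result and contact chances are equal and independent. The sensitivity, specificity, true rates and contact model are assumptions. The conflict between sections and the lower attempt count do not depend on them.

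**What to change.** In Protocol 8.1.6, state that interviewer calls (up to five attempts, with a home visit where there is no phone) are the only source of day-7 outcomes for every Phase 1 child. Bring the synopsis, Protocol 4.1 and 7.1, and SAP 2.1.2 and 3.1 into line with that.

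Run automated calls and SMS in Phase 1 only in parallel, stored separately and not used as outcome data.

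Base any switch for Phase 2 on two pre-stated quantities instead of overall agreement: the share of interviewer-reported failures that the automated system also reports, with its 95% confidence interval, and the response rate among all caregivers contacted.

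The cost is a few lines of protocol text, since interviewer follow-up of all Phase 1 children is already the default. The downside is that any call-centre saving from an early switch is forgone.

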#### **8.1.7 Unique study identification number**

Patients will be given a unique study identification number through a QR code that will be placed into the patient medical record booklet, vaccination card, or another document they are likely to carry with them each time they visit the HF. The ID labels will be pre-printed in bulk (specific to the district and HF) and delivered to the facilities. The label will be scanned using a QR code reader in the tablet each time the child presents at a HF. In the registration module on the tablet, an advanced search system will be created that uses the study ID number, the name of the child, the name of the mother or father or caregiver and the date of birth, so that the child can be identified with certainty with or without their ID label, and former consultations, if any, can be retrieved and linked to the new consultation. Provisions will be made to replace lost IDs if necessary and to store multiple IDs for the same patient.

#### **8.2 Objective 2: Adapt the algorithm to epidemiological and demographic conditions**

In Phase 2 of the study, the algorithm will be improved in terms of diagnostic and prognostic accuracy and adapted to local fluctuations in epidemiology, demography, geography and resource availability.

Each potential modification will first be evaluated by the Rwandan clinical expert group for its clinical coherence, safety and potential benefit, and then applied to the retrospective data. If these analyses confirm a clinically relevant positive impact, the change in the algorithm will be implemented in all relevant locations/patient sub-groups and monitored based on the indicators relevant to the specific change in the algorithm collected throughout the study through the tablets.

### 8.3 Objective 3: Enhance M&E and supportive supervision

All data generated by ePOCT+ will be anonymized and sent to a central sever. Data will be visualized through the medAL-monitor/medAL-outbreak dashboard made available to district health authorities using the key indicators they will have chosen together with the M&E focal points (with as much overlap with the routine HMIS indicators as possible). The medAL-monitor/medAL-outbreak platform will then be installed on the PC or tablet of individuals who normally monitor data and/or conduct supervision to HFIs. These users will be trained on how to use the tool and interpret trends in the indicators for decision-making. HWs and facility in-charges will also receive training on how to monitor their clinical practices at the individual and facility levels, perform self-audits, and build internal capacity and culture of quality improvement. Feedback from all users on the interface and their experience using the platform will be solicited throughout the project and the interface improved.

Furthermore, thresholds for the detection of abnormalities in the data will be integrated into the medAL-outbreak system to enable health authorities to investigate if the cause of abnormal trends in the syndromic surveillance data is due to local epidemic or another reason. For example, a sudden increase in malaria cases could be due to a problem with the quality of the batch of mRDTs used. These thresholds for the indicators of interest will be developed together with the district team to match their needs and interests.

### 8.4 Objective 4: Create a supportive environment for the use of clinical algorithms and supporting tools

#### 8.4.1 Stakeholder engagement

Prior to implementation, the study will be presented to different partners and key actors in the Rwandan health sector through the Health Sector Working Group, Maternal and Child Health Technical Working Group, eHealth Technical Working Group, and the steering committee set up by the MoH to supervise and oversee the implementation of the project. The study protocol will also be presented and approved by the targeted district hospitals and regular meeting with other partners working in the targeted districts will be given regular updates on the project implementation.

Stakeholders will contribute to the content of key documents and give feedback on the planned activities. If needed, international experts can be invited at certain time points. The stakeholder group might evolve over time but the initial composition will include experts in child health, steering committee members, members of the technical working group, district hospitals and other who will be designated by the MoH and RBC.

Members of the community will also be involved throughout the study. Meetings with community leaders will be held in convenient locations to encourage participation. In initial study introduction meetings, community leaders will be informed of the study and asked to disseminate the information to their communities. Subsequently, wider community meetings will be held to solicit feedback about the intervention throughout the study period. Lastly, FGDs will allow community members to formally participate in the study.

#### 8.4.2 Capacity building

DYNAMIC project aims to enhance partnerships with higher learning institutions to ensure the sustainability of the project and to encourage the development of highly skilled medical and research

community in Rwanda. Sustainability of the intervention will be evaluated by assessing the level of local human capacities that will have been reached at the end of the study in terms of: 1) clinical competencies by HWs; 2) clinical algorithm creation by medical experts; 3) software and IT infrastructure maintenance by informatics professionals; 4) M&E capacity and use of data for decision-making by district health authorities and; 5) ML analysis by data scientists.

#### 8.4.3 Development of frameworks for future scale-up of the e-POCT+ intervention

During the last year of the DYNAMIC project, we will develop for the Rwandan national and district health authorities, as the ultimate owners and users of ePOCT+ and its data, the necessary tools for further national scale-up. These tools will include but are not limited to:

- An optimized version of the software allowing health authorities to modify the electronic algorithms without the help of software programmers whenever they need (medAL-creator). This software application will allow clinical experts to create, maintain and update any type of algorithm aimed at guiding HWs during a patient consultation, whatever the age or medical condition. It will also include a feature to deploy or export a new version of the algorithm into all tablets located at the HF. Through an intuitive interface, the user will be able to draw the medical algorithm by dragging and dropping some predefined elements such as exposures, signs, symptoms and diagnostic tests.
- A manual for local experts on the evidence-based path that needs to be followed to adapt and update the algorithm's medical content.
- A document on the best practices for the application of ML to clinical big data.
- A manual of implementation guidelines, standard operating procedures and training materials for various components of the ePOCT+ intervention.
- To the extent possible, interoperability guidelines will be developed for the prevailing eHealth tools with which ePOCT+ could be integrated. Examples include, but are not limited to, aggregation of patient level data from ePOCT+ for automated reporting into the DHIS2 platform, or linkage of ePOCT+ with the electronic medical records systems such as OpenClinic or OpenMRS so that information from patient encounters managed using ePOCT+ can be stored in the patients' medical record.

Support to health authorities willing to develop implementation guidelines that take into account the facilitators and barriers discovered during the project will be provided upon request. To be able to ensure maintenance of the medAL-creator open-source software in the long term, Unisanté is presently considering creating a non-profit foundation linked to Unisanté that would provide low-cost implementation consulting services for low-income countries or public entities, with the aim of reaching the largest possible number of patients with this public good.

